### 2.1.1.6 On-treatment assessment/event and observation periods

For all safety analyses, the overall observation period will be divided into three mutually exclusive segments:

- ***pre-treatment period***: from day of patient's informed consent to the day before first administration of study treatment
- ***on-treatment period***: from date of first administration of study treatment to 30 days after date of last actual administration of any study treatment (including start and stop date)
- ***post-treatment period***: starting at day 31 after date of last administration of study treatment

If dates are incomplete in a way that clear assignment to pre-, on-, post-treatment period cannot be made, then the respective data will be assigned to the on-treatment period.

Safety summaries will primarily include only data from the on-treatment period. Select summaries of related adverse events and death will be produced for the combined on-treatment and post-treatment periods of study treatment (see [Section 2.8.1](#) and [Section 2.8.2](#)).

### 2.1.1.7 Last contact date

The last contact date will be derived for patients not known to have died at the analysis cut-off using the last complete date among the following:

**Table 2-1      Last contact date data sources**

Source data	Conditions
Last contact date/last date patient was known to be alive from Survival eCRF page	Patient status is reported to be alive or unknown in the survival eCRF page
Start/End dates from further antineoplastic therapy	Non-missing medication/procedure term.
Start/End* dates from study treatment eCRF	Non-missing dose. Doses of 0 are allowed.

Source data	Conditions
End of treatment date from end of treatment page	No condition.
Tumor (RECIST) assessment date	Evaluation with a response.
Date of verification for treatment beyond RECIST 1.1 PD	Will the subject continue treatment beyond disease progression as per RECIST 1.1? marked as 'Yes'
PK collection dates	Was sample taken marked as 'Yes'.
Vital signs/ECGs/Laboratory date	At least one non-missing parameter value
Performance Status date	Non-missing performance status
Start/End dates of AE	Non-missing verbatim term

The last contact date is defined as the latest complete date from the above list on or before the data cut-off date. The cut-off date will not be used for last contact date unless the patient was seen or contacted on that date. No date post cut-off date will be used. Completely imputed dates (e.g., the analysis cut-off date programmatically imputed to replace the missing end date of a dose administration record) will not be used to derive the last contact date. Partial date imputation is allowed for event (death)/censoring is coming from 'Survival information' eCRF.

The last contact date will be used for censoring of patients in the analysis of time to event endpoints.

## 2.2 Analysis sets

### Full Analysis Set (FAS)

The Full Analysis Set (FAS) comprises all subjects to whom study treatment has been assigned and who received at least one dose of study treatment (i.e., at least one dose of any component of the study treatment that is capmatinib or spartalizumab (including incomplete infusion)).

### Safety Analysis Set (SS)

The FAS and Safety Set are identical.

### Capmatinib Pharmacokinetic analysis sets (INC-PAS and INC-FPAS)

The capmatinib PAS includes two sets, the capmatinib pharmacokinetic analysis set (INC-PAS) and capmatinib full pharmacokinetic analysis set (INC-FPAS) which will be used for non-compartmental analysis (NCA).

The INC-PAS includes all subjects who have provided at least one evaluable capmatinib PK concentration. For a capmatinib PK concentration to be evaluable, a subject must:

- Have taken a dose of capmatinib prior to sampling

- For pre-dose samples, do not vomit within 4 hours after the dosing of capmatinib prior to sampling.
- For post-dose samples, do not vomit within 4 hours after the dosing of capmatinib
- For pre-dose sample, have the sample collected before the next dose administration and 9-15 hours after the last dose administration.

The INC-FPAS includes all INC-PAS subjects who have provided a capmatinib evaluable PK profile on cycle 3 day 1 (only applicable to subjects with extensive PK sampling). A capmatinib PK profile is considered evaluable if all of the following conditions are satisfied:

- Subject has received one dose of the planned capmatinib treatment
- Subject has provided at least one valid primary PK parameter
- Subjects did not vomit within 4 hours after the dosing of capmatinib

### **Spartalizumab Pharmacokinetic analysis sets (PDR-PAS and PDR-FPAS)**

The spartalizumab PAS includes two sets, spartalizumab pharmacokinetic analysis set (PDR-PAS) and spartalizumab full pharmacokinetic analysis set (PDR-FPAS).

The PDR-PAS includes all subjects who have provided at least one evaluable PK concentration. For a concentration to be evaluable, a subject must:

- Have received one of the planned doses (complete infusion) of spartalizumab prior to sampling.
- For pre-dose samples, have the sample collected before the next dose administration.

The PDR-FPAS includes all subjects who provide an evaluable PK profile (Note: Only applicable to subjects with extensive PK sampling). A profile is considered evaluable if all of the following conditions are satisfied:

- Subject has received one dose (complete infusion) of the planned spartalizumab treatment
- Subject has provided at least one valid primary PK parameter
- For pre-dose samples, have the sample collected before the next dose administration.

Only PK blood samples with date and time and for which the last prior dose dates and times are adequately recorded will be included in the PK analyses.

Any blood samples with missing collection date or time or missing associated study drug dosing date or time will be excluded. Additionally, a PK sample can be considered not evaluable as per scientific judgment of the clinical pharmacology expert. In such case, the PK sample is excluded from the analyses and the reason for its exclusion will be documented.

## 2.2.1 Classification of subjects

Subjects may be excluded from the analysis populations defined above based on the protocol deviations (PD) entered in the database and/or on specific classification rules defined in [Table 2-2](#).

**Table 2-2 Subject classification based on PDs and non-PD criteria**

Analysis set	Protocol deviations leading to exclusion	Non protocol deviation leading to exclusion
Full analysis set	No written inform consent	Subject not receiving a dose of study treatment
Safety set	No written inform consent	Subject not receiving a dose of study treatment
INC-PAS and PDR-PAS	No written informed consent C1D1 Spatalizumab PK sample not collected or collected after dosing	Subject not receiving a dose of study treatment Subject not providing any evaluable PK concentration for capmatinib or spatalizumab, respectively
INC-FPAS and PDR-FPAS	No written informed consent C1D1 Spatalizumab PK sample not collected or collected after dosing	Subject not receiving a dose of study treatment Subject not providing a valid PK profile for capmatinib or spatalizumab, respectively

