#### 8.5.2.2 Pharmacokinetic sampling for capmatinib

PK blood samples for capmatinib will be collected for all the subjects as outlined in [Table 8-7](#) and [Table 8-8](#). Extensive PK samples will be collected on cycle 3 day 1 from the first fifteen subjects enrolled in Part 1.

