#### Pharmacokinetic Analysis Set (PAS)

The capmatinib PAS includes two sets in Part 1, the capmatinib full pharmacokinetic analysis set (INC-FPAS) which will be used for NCA analysis and capmatinib pharmacokinetic analysis set (INC-PAS).

The INC-FPAS includes all subjects who have provided an evaluable PK profile (only applicable to subjects with extensive PK sampling). A profile is considered evaluable if all of the following conditions are satisfied:

- Subject has received one dose of the planned capmatinib treatment
- Subject has provided at least one valid primary PK parameter
- Subjects did not vomit within 4 hours after the dosing of capmatinib

The INC-PAS includes all subjects who have provided at least one evaluable PK concentration. For a concentration to be evaluable, a subject must:

- Have taken a dose of capmatinib prior to sampling
- For pre-dose samples, do not vomit within 4 hours after the dosing of capmatinib prior to sampling.
- For post-dose samples, do not vomit within 4 hours after the dosing of capmatinib
- For pre-dose sample, have the sample collected before the next dose administration and 9-15 hours after the last dose administration.

The spartalizumab PAS includes two sets in Part 1, spartalizumab full pharmacokinetic analysis set (PDR-FPAS) and spartalizumab pharmacokinetic analysis set (PDR-PAS).

The PDR-FPAS includes all subjects who provide an evaluable PK profile (Note: Only applicable to subjects with extensive PK sampling). A profile is considered evaluable if all of the following conditions are satisfy:

- Subject has received one dose (complete infusion) of the planned spartalizumab treatment
- Subject has provided at least one valid primary PK parameter
- For pre-dose samples, have the sample collected before the next dose administration.

The PDR-PAS includes all subjects who have provided at least one evaluable PK concentration.

For a concentration to be evaluable, a subject must:

- Have received one of the planned doses (complete infusion) of spartalizumab prior to sampling.
- For pre-dose samples, have the sample collected before the next dose administration.

[REDACTED]

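### SAP Table 2-2 lets a spartalizumab sampling lapse remove subjects from the capmatinib PK sets, which SAP 2.2 and Protocol 12.1 define by capmatinib conditions alone

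*SAP*

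**What the plan says.** SAP 2.2 sets the capmatinib populations by capmatinib criteria. For the concentration set: "The INC-PAS includes all subjects who have provided at least one evaluable capmatinib PK concentration". For the profile set: "The INC-FPAS includes all INC-PAS subjects who have provided a capmatinib evaluable PK profile on cycle 3 day 1". Protocol 12.1 agrees on the basis for membership: "The INC-PAS includes all subjects who have provided at least one evaluable PK concentration" and, for profiles, "The INC-FPAS includes all subjects who have provided an evaluable PK profile (only applicable to subjects with extensive PK sampling"). The listed conditions concern having taken capmatinib, not vomiting within 4 hours of the dose, the 9 to 15 hour window for pre-dose samples, and having at least one valid primary PK parameter. None mentions spartalizumab.

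SAP 2.2.1 then adds a second layer: "Subjects may be excluded from the analysis populations defined above based on the protocol deviations (PD) entered in the database" and/or on the rules in Table 2-2. In that table the PK sets appear in two combined rows, INC-PAS with PDR-PAS and INC-FPAS with PDR-FPAS. In both rows the protocol-deviation column contains "C1D1 Spatalizumab PK sample not collected or collected after dosing". The next column of the concentration-set row does assign its condition by drug: "Subject not providing any evaluable PK concentration for capmatinib or spatalizumab, respectively". The profile-set row does the same.

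**The concern.** A missed or late spartalizumab sample on the first day of treatment says nothing about whether a later capmatinib concentration is valid, and the SAP gives no reason for linking them. Taken literally, Table 2-2 nevertheless makes it a ground for removing the subject from both capmatinib sets.

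Capmatinib PK is part of a secondary objective (SAP Table 1-1). INC-PAS supplies the concentration summaries and INC-FPAS the AUC, Cmax and Tmax summaries (SAP 2.9). Two things are at stake: valid data could be left out, and two programmers could build different capmatinib sets while each follows the SAP. Nothing in SAP 2.2.1 says when the permission to exclude should be used.

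**Working it through.** The plan states no figure on this point to reproduce. The check compares the rules and then counts samples.

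**1. Same subject, three rules.** Take a subject with no C1D1 spartalizumab sample, or one drawn after dosing, who has evaluable capmatinib samples at C3D1 and C4D1.

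| Rule | INC-PAS | INC-FPAS (if on extensive sampling with an evaluable profile) |
|---|---|---|
| Protocol 12.1 | in | in |
| SAP 2.2 | in | in |
| SAP Table 2-2 | may be excluded | may be excluded |

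The subject can leave INC-FPAS by two routes. The deviation is listed directly in the INC-FPAS row. In addition, SAP 2.2 draws INC-FPAS from INC-PAS subjects, so removal from INC-PAS carries over.

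**2. Timing.** Protocol 8.5.2.2 says that "PK blood samples for capmatinib will be collected for all the subjects as outlined in" Tables 8-7 and 8-8. Those tables schedule capmatinib samples at C3D1 and C4D1 only, and none at C1D1. With 28-day cycles, C3D1 falls 2 × 28 = 56 days after C1D1. The C1D1 spartalizumab sample is therefore not part of any capmatinib profile.

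**3. Scheduled capmatinib samples at risk per excluded subject** (unscheduled samples not counted)

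- Extensive sampling, Table 8-7: C3D1 pre-dose, 1, 2, 4 and 8 h = 5; C4D1 pre-dose and one within 1–4 h = 2. Maximum 5 + 2 = 7.
- Non-extensive sampling, Table 8-8: C3D1 = 2; C4D1 = 2. Maximum 2 + 2 = 4.
- The minimum is 1 in either case, because a subject needs at least one evaluable concentration to be in INC-PAS at all.

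The loss falls below the maximum if the subject stopped before C4D1, vomited within 4 hours of dosing or missed the 9 to 15 hour pre-dose window.

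**4. Profiles.** Extensive sampling is planned for the first 15 subjects of Part 1. One lost profile is therefore at least 1/15 = 6.7% of the profiles that could exist.

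**5. Number of subjects.** The documents do not say how many subjects have this deviation. Three of the 28 + 3 = 31 subjects started on capmatinib alone after the enrolment halt, so they would have no pre-infusion C1D1 sample. With no infusion planned for them, it is not evident that the missing sample would be recorded as a deviation. They are not relied on as a count here.

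**The case against.** The best defence is that the item was meant for the spartalizumab sets only. It names that drug, the neighbouring column assigns conditions by drug, and the capmatinib definitions in SAP 2.2 are explicit. The rule is also permissive: subjects may be excluded, not must be. Table 2-2 adds other conditions that the definitions lack, such as written consent for the FAS, so an added condition is not in itself a contradiction. Any exclusion would be visible, because set membership is summarised and listed (SAP 2.3.6). The dataset specifications, which are a separate document, might settle the matter. Finally, capmatinib PK is descriptive and already allows case-by-case removal of samples (SAP 2.2 and 2.9.1).

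The drafting-shortcut reading is plausible, and together with the permissive wording it lowers the likely impact. It does not remove the problem. The drug qualifier appears in one column and is missing from the other, so the table itself does not confine the item to the spartalizumab sets. The consent parallel is weak: consent bears on any use of a subject's data, whereas a spartalizumab sample has no evident bearing on a capmatinib set. The provisions in SAP 2.2 and 2.9.1 act on samples, concentration data and parameter estimation, and neither limits the Table 2-2 item to one drug. Listing the exclusions shows them after the fact but does not say which rule applies. The separate specifications cannot be assumed to resolve it.

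**Conclusion.** The concern holds. As written, Table 2-2 permits exclusion from INC-PAS and INC-FPAS on a criterion that neither SAP 2.2 nor Protocol 12.1 contains. It is worth correcting, with bounded impact: 1 to 7 (extensive) or 1 to 4 (non-extensive) scheduled capmatinib concentrations per excluded subject, plus one profile where the subject qualifies for INC-FPAS. The number of subjects is unknown and may be zero.

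The effect is confined to descriptive capmatinib PK; the FAS, the Safety Set, ORR, DCR, PFS and safety are unaffected. The conclusion rests on reading the shared rows literally. If the sponsor intended the item for the spartalizumab sets only, the correction merely records that intention. No conclusion is drawn here about whether the item suits the spartalizumab sets.

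**What to change.** Split the two combined PK rows of Table 2-2 into four, one each for INC-PAS, PDR-PAS, INC-FPAS and PDR-FPAS, and omit the C1D1 spartalizumab item from the INC-PAS and INC-FPAS rows. The capmatinib rows would then carry only the consent, dosing and capmatinib evaluability conditions, in line with SAP 2.2 and Protocol 12.1. The PDR-PAS and PDR-FPAS criteria are outside this point and can stay as they are. SAP section 4 needs no entry on this account, because the change removes a departure from the protocol.

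The cost is an edit to two table rows, with no new data and no new derivation.

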## 2.2.2 Withdrawal of inform consent

Any data collected after a subject withdraws informed consent from all further participation in the study, will not be included in the analysis. Data collected on the same date as withdrawal of informed consent are reported. The date on which a subject withdraws full consent is recorded in the eCRF.

## 2.2.3 Subgroup of interest

Not applicable

## 2.3 Patient disposition, demographics and other baseline characteristics

Summaries and listings described in this section will be based on the FAS.

### 2.3.1 Patient disposition

The number (%) of treated subjects included in the FAS will be presented. The number (%) of screened and not-treated subjects.

The following summaries will be tabulated:

- Number (%) of subjects treated.

- Number (%) of subjects who are still on-treatment at the time of cut-off (to be removed at time of final CSR).
- Number (%) of Subjects who discontinued study treatment and primary reasons for discontinuation.
- Number of (%) Subjects followed up/not followed after discontinuation of study treatment and reasons for post-treatment follow-up discontinuation.

### **2.3.2 Demographic**

Demographic data and other baseline characteristics data (including age, sex, race, ethnicity, height, weight, ECOG performance status, smoking history) will be listed and summarized. In addition, following age categories will be summarized: 18- <65 years, 65- < 85 years, and  $\geq$  85 years.

### **2.3.3 Medical history**

A listing of medical history and current medical conditions will be provided, using the latest Medical Dictionary for Regulatory Activities (MedDRA) terminology available at the time of reporting.

### **2.3.4 Diagnosis and extent of cancer**

The summary and listing of diagnosis and extent of cancer (disease history) will include: details of tumor histology/cytology, histologic grade, stage at initial diagnosis, stage at time of study entry, types of lesions at baseline, current extent of disease (metastatic sites), and PD-L1 expression at baseline.

Imputation rules for partially missing dates are provided in [Section 5.1.3.3.1](#).

### **2.3.5 Protocol deviations**

The FAS will be used for the protocol deviation summary tables and listing. The number (%) of patients with any CSR-reportable protocol deviation will be tabulated by the deviation category.

### **2.3.6 Analysis sets**

The number (%) of patients in each analysis set (defined in [Section 2.2](#)) will be summarized and listed.

## **2.4 Treatments (study treatment, concomitant therapies, compliance)**

### **2.4.1 Study treatment / compliance**

Duration of exposure, actual cumulative dose, dose intensity (DI) and relative dose intensity (RDI) will be summarized separately for each component of study treatment. Duration of exposure will also be calculated for the study treatment.

Duration of exposure will be categorized into time intervals (e.g., <6 weeks, 6 - <12 weeks, 12 - <18 weeks, 18 - <24 weeks, 24 - < weeks, 48 - <72 weeks and >72 weeks); frequency counts and percentages will be presented for the number (%) of subjects in each interval. Continuous summarized for duration of exposure will be provided using weeks as time units.

The number (%) of subjects who have dose adjustment (only reductions will be summarized in the analysis) or interruptions, and the reasons, will be summarized for all subjects. Subject level listings of all doses administered on treatment along with dose change reasons will be produced.

The safety set will be used for all summaries and listings of study treatment.

#### **2.4.1.1 Duration of exposure for investigational drug**

Duration of exposure to capmatinib (days) = (last date of exposure to capmatinib) – (date of first administration of capmatinib) + 1.

With:

1. The first date of exposure for capmatinib is the first date when a non-zero capmatinib dose was administered and recorded on the study treatment eCRF.
2. The last date of exposure to capmatinib is the end date from the last dose administration record non-zero capmatinib dose is recorded in the study treatment eCRF.

Duration of exposure to spartalizumab (days) = (last date of exposure to spartalizumab) – (date of first administration of spartalizumab).

With:

1. The first date of exposure for spartalizumab is the first date when a non-zero spartalizumab dose was administered and recorded on the study treatment eCRF.
2. The last date of exposure to spartalizumab is the end date from the last dose administration record non-zero spartalizumab dose is recorded in the study treatment eCRF + 27 days (if no death or no lost to follow-up is observed).
3. The last date of exposure to spartalizumab is the earliest date among last dose administration record non-zero spartalizumab dose + 27 days and date of death if the subject died.
4. The last date of exposure to spartalizumab is the earliest date among last dose administration record non-zero spartalizumab dose + 27 days and date of last contact date if the subject was lost to follow-up.

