#### **2.4.1.2 Cumulative dose**

Cumulative dose of a study treatment is defined as the total dose given during the study treatment exposure and will be summarized for each of the study treatment components, respectively.

The planned cumulative dose for a study treatment component refers to the total planned dose as per the protocol up to the last date of investigational drug administration. The planned cumulative dose is not summarized/listed. It is used for relative dose intensity calculations.

The actual cumulative dose refers to the total actual dose administered, over the duration for which the subject is on the study treatment as documented in the study treatment eCRF.

For subjects who did not take any drug, the actual cumulative dose is by definition equal to zero for that drug.

For capmatinib (continuous dosing), the actual cumulative dose is the sum of the non-zero doses recorded over the dosing period. The planned cumulative dose is the planned starting dose summed over the same dosing period.

For spartalizumab (intermittent dosing), the actual cumulative dose should be defined based on the days when the subject is assumed to have taken a non-zero dose during dosing periods (number of infusions taken over the treatment period). The planned cumulative dose is the planned starting dose summed over the number of expected infusions during treatment period (e.g, a subject treated for 60 days is expected to have three infusions).

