#### 2.4.1.3 Dose intensity and relative dose intensity

For dose intensity calculations, the unit of time for capmatinib will be days and for spartalizumab will be cycles.

For capmatinib, the **dose intensity** (DI) is defined as follows:

DI (mg / days) = Actual Cumulative dose (mg) / Duration of exposure to capmatinib (days).

For example:

The duration of exposure is 56 days and the subject received 50 days of full dosing

DI (mg/day) = 40 000 (mg) / 56 (Day) = 714 (mg/day)

For spartalizumab, the **dose intensity** (DI) is defined as follows:

DI (mg / cycles) = length of cycle \* (Actual Cumulative dose (mg) / duration of exposure to spartalizumab (days)).

For example:

The duration of exposure is 56 days and the subject received two complete infusions

DI (mg/cycle) = 28 (days) \* (800 (mg) / 56 (days)) = 400 (mg/cycle)

For subjects who did not take any drug the DI is by definition equal to zero.

For capmatinib, the **Planned dose intensity** (PDI) is defined as follows:

PDI (mg / days) = Planned Cumulative dose (mg) / Duration of exposure to capmatinib (days)

For example:

The duration of exposure is 56 days, and the subject is planned to receive 56 days of dosing

PDI (mg/day) = 44 800 (mg) / 56 (Day) = 800 (mg/day)

For spartalizumab, the **Planned dose intensity** (PDI) is defined as follows:

PDI (mg / cycles) = length of cycle \* (Planned Cumulative dose (mg) / duration of exposure to spartalizumab (days)).

For example:

The duration of exposure is 56 days, and the subject is planned to receive two infusions

PDI (mg / cycles) = 28 (days) \* (800 (mg) / 56 (days)) = 400 (mg/cycle)

**Relative dose intensity (RDI)** is defined as follows:

RDI = DI (mg / unit of time) / PDI (mg / unit of time)

DI and RDI will be summarized separately for each of the study treatment components, using the duration of exposure of each of the components. RDI will be summarized in percentages. Summary of RDI includes categorical summaries. The RDI categories are < 50%, ≥ 50% - < 75%, ≥ 75% - < 90%, ≥ 90% - < 110% and ≥ 110%.

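### The spartalizumab exposure formula omits the +1 used for capmatinib, so it contradicts the SAP's 56-day example and overstates on-schedule dose intensity

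*SAP*

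**What the plan says.** SAP 2.4.1.1 gives one duration formula per drug:

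- Capmatinib: "Duration of exposure to capmatinib (days) = (last date of exposure to capmatinib) – (date of first administration of capmatinib) + 1".
- Spartalizumab: "Duration of exposure to spartalizumab (days) = (last date of exposure to spartalizumab) – (date of first administration of spartalizumab", with nothing added.

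The last spartalizumab exposure date is the last non-zero infusion plus 27 days. It is cut short at death ("earliest date among last dose administration record non-zero spartalizumab dose + 27 days and date of death if the subject died") and, in the same way, at last contact for subjects lost to follow-up.

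SAP 2.4.1.3 defines spartalizumab DI as 28 times the actual cumulative dose divided by this duration. Planned dose intensity (PDI) is built in the same way from the planned dose, and RDI is DI divided by PDI. Its DI example starts from "The duration of exposure is 56 days and the subject received two complete infusions" and arrives at 400 mg/cycle. The PDI example also pairs 56 days with two infusions and also gives 400.

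On the planned dose, SAP 2.4.1.2 speaks first of the "total planned dose as per the protocol up to the last date of investigational drug administration". For spartalizumab it then says: "The planned cumulative dose is the planned starting dose summed over the number of expected infusions during treatment period", with the illustration that "a subject treated for 60 days is expected to have three infusions". SAP 2.4.1.3 adds that DI and RDI are summarised per component, "using the duration of exposure of each of the components".

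**The concern.** A 27-day tail completes a 28-day cycle only if the first and last days are both counted. The capmatinib formula counts both and the spartalizumab formula does not. The stated rule and the stated example therefore disagree, and a programmer following 2.4.1.1 will not reproduce 2.4.1.3.

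Dose intensity is a named tolerability measure in SAP Table 1-1, and enrolment was halted because the combination was not tolerated. A subject who received every infusion on time should show 400 mg/cycle.

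A related ambiguity sits next to it. Planned infusions are counted over a period whose end is not tied to spartalizumab. SAP 2.1.1.1 lets *investigational drug* mean either agent, and ongoing subjects stopped spartalizumab but continued capmatinib (protocol Amendment 1, Study Update).

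**Working it through.** **Inputs.** Spartalizumab 400 mg every 28 days (protocol 6.1.3), so infusions fall due on days 1, 29, 57 and so on. Tail of 27 days and the duration formulas from SAP 2.4.1.1. DI, PDI and RDI from SAP 2.4.1.3. On-treatment visit window of ±3 days (protocol section 8).

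**The SAP's own figures.**
- Capmatinib DI: 50 days × 800 mg = 40,000 mg; 40,000 / 56 = 714 mg/day. Reproduced.
- Spartalizumab DI once 56 is inserted: 28 × 800 / 56 = 400 mg/cycle. Reproduced.
- Spartalizumab duration by the formula, infusions on days 1 and 29: last date = 29 + 27 = day 56; 56 − 1 = 55 days. **Not reproduced.** With +1 it is 56.

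**Effect on DI.** For n on-schedule infusions the duration is 28n − 1 as written and 28n with +1, so DI as written is 28 × 400n / (28n − 1).

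| Infusions | Days as written | DI as written | Days with +1 | DI with +1 |
|---|---|---|---|---|
| 1 | 27 | 414.8 | 28 | 400 |
| 2 | 55 | 407.3 | 56 | 400 |
| 3 | 83 | 404.8 | 84 | 400 |
| 6 | 167 | 402.4 | 168 | 400 |
| 12 | 335 | 401.2 | 336 | 400 |

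The excess is 3.7% for one infusion (28/27), 1.8% for two (56/55) and 1.2% for three (84/83).

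**Effect on exposure categories (SAP 2.4.1).** Three on-schedule infusions give 83 days, which is below 12 weeks, instead of 84. Six give 167 days, below 24 weeks, instead of 168.

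**Zero duration.** If death or last contact falls on the day of the only infusion, first and last dates coincide. The duration is 0 and DI cannot be computed.

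**Effect on RDI.** DI and PDI share the same divisor, so RDI = actual dose / planned dose. For a fixed planned dose the missing day cancels.

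**Planned infusions.** The number due by day D is floor((D − 1)/28) + 1. Take two infusions, the second 2 days late on day 31, which is inside the visit window:
- Counted to the last infusion (day 31): floor(30/28) + 1 = 2 planned; RDI = 2/2 = 100%.
- Counted over spartalizumab exposure as written (31 + 27 − 1 = 57 days): floor(56/28) + 1 = 3 planned; RDI = 2/3 = 66.7%.
- Counted to the last dose of either drug, if capmatinib ran an assumed 168 days: floor(167/28) + 1 = 6 planned; RDI = 2/6 = 33.3%. At an assumed 336 days it is 2/12 = 16.7%.

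The three readings put this subject in three different RDI categories (≥90% to <110%, ≥50% to <75%, <50%).

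**Interaction.** Suppose the second infusion is only 1 day late (day 30). On the exposure reading the duration is 56 days as written, so 2 are planned. With +1 it is 57 days, so 3 are planned. Adding +1 without settling the counting period therefore brings the extra planned infusion forward by a day.

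**The case against.** The strongest reply is that the slip is small and descriptive. It adds at most 3.7% to an on-schedule DI, shrinks with each infusion and leaves RDI unchanged for a fixed planned dose. All of that stands.

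The DI example also gives no infusion dates, and a second infusion one day late would yield 56 days under the written formula (30 + 27 − 1). That does not rescue the PDI example. It describes the planned schedule, where two infusions 28 days apart fill 56 days only on an inclusive count.

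Three stronger readings are tempting but not supported:

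- *The counting period has no definition at all.* SAP 2.4.1.2 does give an end point. What is missing is which drug it refers to and how it relates to the treatment period named for spartalizumab. The low RDI values above are consequences of particular readings, not errors shown in the plan. The 60-day illustration (three infusions due) is correct and does not settle the matter. The programming specification, which is not among the documents, may do so.
- *The range of DI error across the trial is known.* Infusion counts per subject are not given, so only case-by-case figures can be stated.
- *Scoring never-dosed subjects as zero is a mistake.* SAP 2.4.1.2 and 2.4.1.3 set cumulative dose and DI to zero for subjects who took no drug. By the protocol's Study Update, 3 of 31 subjects started on capmatinib alone, so the zeros lower mean spartalizumab DI by 3/31 = 9.7%. That follows a stated convention. The only real gap is that their RDI is 0/0 with no rule.

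**Conclusion.** The concern holds for the missing +1. SAP 2.4.1.1 and the examples in 2.4.1.3 cannot both be followed. As written, on-schedule DI is 414.8, 407.3 and 404.8 mg/cycle for one, two and three infusions instead of 400. These figures assume full 400 mg infusions on schedule and exposure not cut at death or last contact.

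A reader might infer that adding +1 makes DI sound for every subject. It does not. For one infusion and death on day 10, the cut exposure gives 28 × 400 / 9 = 1,244 mg/cycle as written and still 28 × 400 / 10 = 1,120 with +1. That follows from the rule cutting exposure at death, not from the missing day.

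The planned-infusion wording needs clarifying. It is not a demonstrated error, and the 33.3% figure rests on the assumed 168 days of capmatinib.

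Neither matter reaches ORR, DCR or PFS.

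**What to change.** 1. In SAP 2.4.1.1, add +1 to the spartalizumab duration formula.
2. In the same edit, state in 2.4.1.2 which drug's last administration date ends the period for counting planned spartalizumab infusions, and whether the 27-day tail is included. The choice is the sponsor's, but it must be written down, because the +1 shifts the count on the exposure reading.
3. Optionally, report how many Safety Set subjects never received spartalizumab (3 by the protocol's Study Update), and show spartalizumab DI and RDI in dosed subjects.

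The cost is a few sentences in the SAP and a few lines of code. No new data are needed. Under the SAP's own Introduction, the change is an amendment if made before database lock and an addendum if made after.
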